#### 3.2. Details of the trial design

The trial is designed to integrate with rather than replace the normal clinical care of participants. For most participants the investigator will be their consultant psychiatrist (or a member of his/her team). Where this is the case, the investigator retains overall responsibility for the clinical care of the participant and should always act in the participant's best interests. This includes ensuring that the clinical investigations recommended by the NICE guidelines on bipolar disorder for initiating and continuing trial treatments are carried out (NICE, 2006). The investigator should assess adherence to treatment and monitor levels of trial drugs according to normal practice and should undertake any other investigations that are clinically indicated. Where the investigator is not a member of the participant's clinical team, the consultant retains overall responsibility for the care of the participant and the investigator should liaise with him/her to agree on the activities to be undertaken by the investigator.

Participants will be people with bipolar I disorder or bipolar II disorder who require new pharmacological treatment for an acute depressive episode (see Eligibility Criteria sections 4.1 and 4.2). All participants will initially enter a 7 to 14 day active run-in phase during which they will receive open-label quetiapine monotherapy. The run-in phase will provide immediate treatment to patients with moderate/severe bipolar depression. It will also ensure that only people with depressive episodes of sufficient duration for longer-term and combination treatment to be appropriate are entered into the randomised phase. This stepwise initiation of drugs is consistent with

routine clinical practice and will improve the efficiency of the trial by avoiding early withdrawal from the randomised phase of participants who cannot tolerate quetiapine and/or do not adhere to trial procedures.

At the end of the run-in phase, participants who can tolerate quetiapine, are adhering to trial procedures and remain moderately/severely depressed will be randomised to the addition of lamotrigine or matched placebo, and separately to folic acid or matched placebo. Allocated treatments will be continued for 12 months unless there are clinical reasons to discontinue or consent is withdrawn.

The trial will investigate both short-term (relief from depressive symptoms) and medium/longer-term outcomes (including safety, freedom from depressive and manic symptoms, and tolerability). The randomised phase lasts for one year during which time, participants will be asked to provide weekly self-reports of mood symptoms via short message service (SMS), webform or on paper.

**3.2.1. Informed consent to participate in the trial:** Before any trial specific procedures are performed, the patient must personally sign and date the Informed Consent Form (see section 12.3) using the latest Research Ethics Committee (REC) approved version of the form.

Eligible patients who are currently depressed will be given as long as they would like to decide whether or not to participate in the trial. However, there will often be a clinical need to initiate treatment for depression as soon as possible and therefore immediate entry into the run-in phase will be permitted and, for patients who are already taking quetiapine, immediate entry into the randomised phase. Patients entering the run-in phase will have a minimum of 7 days on open-label standard treatment (i.e. quetiapine) and those entering the randomised phase will have at least 24 hours between consenting to take part and beginning trial treatment.

**3.2.2. Patients who might become eligible for the trial:** The chronic and cycling nature of bipolar disorder means that many patients under the care of trial investigators will experience an acute depressive episode during the recruitment period of the trial. Patients considered by the investigator to be at risk of a depressive episode will, at the investigator's discretion, be informed about the trial, given a Participant Information Sheet and offered the opportunity to express their views on participation. In the event of a depressive episode, patients who have already expressed an interest in the trial will be invited to take part (see section 3.2.1). This process closely resembles routine clinical care where treatment options for future acute episodes may be discussed with patients when they are well to reduce the burden of making treatment decisions when acutely unwell.

**3.2.3. Randomisation:** A randomisation visit should take place between 7 and 14 days after trial entry. If the dose of quetiapine has not been established within 14 days or an appointment cannot be made, the investigator should contact the CEQUEL office to request an extension. The randomisation visit will include checks that the participant is willing to enter the randomised phase and meets the eligibility criteria including uncertainty about optimum treatment.

A centralised randomisation service will be used. Investigators with internet access in their clinic room will access the service via the web. Investigators without internet

---

 If randomisation to folic acid/placebo is not feasible or appropriate, randomisation will be to lamotrigine/placebo only.

access will fax a randomisation form (together with a trial prescription form) to the CEQUEL Office. A member of the CEQUEL team will then perform the randomisation using the centralised system. Each participant will be randomised to either lamotrigine or lamotrigine placebo and also to either folic acid or folic acid placebo.

A non-deterministic minimisation algorithm will be used to produce treatment groups balanced for important prognostic factors. Trial sites will be arranged into geographical regions. The first 60 patients will be allocated randomly without minimisation to avoid predictability. Subsequently, the minimisation algorithm will be applied with an allocation ratio that is not fully deterministic: there will be an 80% bias in favour of allocations that minimise the imbalance.

The randomisation algorithm will minimise for 16 variables related to prognosis at baseline:

- bipolar I or bipolar II (based on DSM-IV criteria)
- baseline severity of depression (QIDS-SR16) – 4 categories: mild ≤10, moderate 11-15, severe 16-20 and very severe ≥ 21
- age – classified as ≤ 30, 31-40, 41-50 and > 50
- gender
- dose of quetiapine (150mg/day; >150 to < 300mg; 300mg/day; >300mg/day)
- concurrent medicines: the algorithm will minimise on each of 7 treatments - lithium, valproate, other mood stabiliser, olanzapine, other atypical antipsychotic, conventional antipsychotic and antidepressant
- pre-screening treatment with quetiapine
- pre- screening treatment with lamotrigine
- number of mood episodes in the past year (< 4 or ≥ 4)
- trial region

Once randomisation has taken place the trial management program will generate a letter to the participant confirming that randomisation has taken place. The letter, prescription form and a list of pack numbers (see section 6.7.1.) will be sent to the trial pharmacy. At the pharmacy the appropriate packs of medicines will be dispensed and sent to the participant (or other agreed recipient) together with the letter. All participants will continue to be prescribed open-label quetiapine according to routine practice.

**3.2.4. Minimisation of Bias:** The centralised randomisation system guarantees complete allocation concealment and prevents subversion of randomisation.

Double-blind investigational treatments will minimise performance and ascertainment biases. Use of placebo to conceal treatments should be effective because neither lamotrigine nor folic acid cause easily recognisable adverse reaction and both are generally well-tolerated.

Multiple methods of minimising loss to follow-up, including telephone follow-up, will be employed to avoid attrition bias. The main statistical analysis will be carried out on the basis of intention-to-treat i.e. after randomisation, data for each participant will be analysed according to the treatment they were allocated irrespective of what treatment they actually received. This removes any elements of subjectivity in deciding whom to include in the analysis (and thus the risk of selection bias).

---

 If randomisation to folic acid/placebo is not feasible or appropriate, randomisation will be to lamotrigine/placebo only.

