- ii) There is also some evidence for a potential interaction between the catechol-o-methyltransferase (COMT) enzyme genotype and response to treatment with folic acid. The COMT gene has a functional SNP (Val158Met) which alters enzyme activity and Val158 homozygotes have been found to have significantly higher levels of homocysteine than Met158 carriers, The COMT effect was independent of, and additive with, the MTHFR 677TT effect (Tunbridge et al. in press).
- iii) Folate hydrolase 1 (FOLH1) facilitates the transfer of dietary folate into the body. Its activity is modulated by a functional variant in its sequence (T484C): the 484T variant has higher activity than the 484C form. Accordingly, the effects of folate supplementation on homocysteine levels and depressive symptoms may be more pronounced in 484TT homozygotes, compared with 484C carriers (Roffman et al 2013).

CEQUEL will investigate the hypothesis that there will be an interaction between folic acid treatment and genotype at these loci. We predict a greater reduction in homocysteine levels – and also depressive symptoms - in 677TT and Val158 homozygotes. In addition, we hypothesise that the impact of folate on biochemical measures (and depressive symptoms) will be more pronounced in FOLH1 484TT homozygotes.

**1.3.6. B12 status:** There is growing evidence of interactions between vitamin B12 status and folate status, with adverse effects of high folate in those with low B12 status. We will also look at baseline B12 status in relation to outcome measures by analysis of total cobalamin and holotranscobalamin [Refsum, 2006b].

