**3.1.2. Secondary outcome measures:**

1. The proportion of participants who both achieve remission by 12 weeks following randomisation (defined as a score of  $\leq 5$  on QIDS-SR16) and remain free from symptomatic relapse by 52 weeks. Depressive relapse is defined as a QIDS-SR16 score  $\geq 10$  on two consecutive weekly ratings and manic relapse as an Altman Self-Rating Mania Scale (ASRM) score of  $\geq 10$  on a single weekly rating.
2. Proportion of time over 12 months when participants were free from manic symptoms (ASRM  $\leq 5$ ).
3. Proportion of time over 12 months when participants were free from depressive symptoms (QIDS-SR16  $\leq 5$ ).
4. New intervention (admission or drug treatment) for manic episode by 52 weeks.
5. New intervention (admission or drug treatment) for depressive episode by 52 weeks.
6. Death (all cause and cause-specific including suicide).
7. Deliberate self-harm.
8. Quality of life – rated using the EuroQol EQ-5D.
9. Unexpected adverse events.
10. Withdrawal from quetiapine or lamotrigine due to adverse effects.
11. Use of health and social care service resources.
12. Social costs/benefits.

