#### **5.8. Emergency procedures for unmasking treatment allocation**

Investigators and participants will be provided with the telephone number for an on-call member of the trial team. This number will operate 24 hours a day 7 days a week and can be used to request unblinding of one or both treatment allocations in the event of a medical emergency. Procedures will be put in place to verify the identity of the participant and caller and the decision on whether to reveal the allocation will be based on a set of criteria for judging clinical need.

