#### **5.9. Unblinding at the end of the trial**

Premature disclosure of allocation risks introducing bias and invalidating the trial results. Masking of treatment allocation will therefore be maintained during the course of the trial unless an adverse event arises that clinically requires disclosure. If a participant formally (in writing to the CEQUEL office) requests disclosure of their treatment allocation, this will be made available to them alone after they have left the trial or at 12 months post-randomisation (whichever is the longer).

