**6. Trial Treatments****6.1. Provision of trial treatments**

Investigators will be responsible for arranging the supply of quetiapine and for using trial prescription forms to prescribe both lamotrigine/placebo and folic acid/placebo according to the dose regimens outlined in sections 6.2 to 6.4. (Recommended rescue medicines are recorded in section 6.5.2.)

Participants will be advised to contact the investigator to report any unexpected occurrence or effect that they think might be related to quetiapine, lamotrigine or folic acid.

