## 7.4. B12 deficiency

In the unlikely event that a participant is found to be B12 deficient (defined as serum level below 150pmol/L), the investigator will be informed and advised about the need for the participant to be prescribed B12 supplementation. No other blood test results will be reported to investigators.

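### Section 3.2 leaves masked investigators free to measure lamotrigine levels, and a measurable result can identify active allocation outside the controlled unmasking route

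*Protocol*

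**What the plan says.** Protocol 3.2 sets out the investigator's duties within normal care. One of them reads: "The investigator should assess adherence to treatment and monitor levels of trial drugs according to normal practice". For most participants the investigator is the consultant psychiatrist or a member of that team. The sentence does not say which drugs it means and does not route any result away from masked staff.

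Other sections protect the masking:

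- Section 3.2.4 relies on it: "Double-blind investigational treatments will minimise performance and ascertainment biases". It argues that placebo will conceal allocation because neither drug produces reactions that are easy to recognise.
- Section 5.8 provides a 24-hour telephone line that "can be used to request unblinding of one or both treatment allocations in the event of a medical emergency". Identity is verified and the request is judged against criteria of clinical need.
- Section 5.9 states: "Masking of treatment allocation will therefore be maintained during the course of the trial unless an adverse event arises that clinically requires disclosure".
- Section 7.4, after providing for B12 deficiency to be notified, states: "No other blood test results will be reported to investigators".

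**The concern.** Placebo tablets conceal allocation from sight and, largely, from symptoms. They do not conceal it from an assay. Section 3.2 gives masked clinicians a general instruction to monitor drug levels, and neither 3.2.4 nor 5.8, 5.9 or 7.4 says what happens when the drug measured is one of the masked ones. An investigator could follow 3.2 in good faith and learn a participant's lamotrigine allocation with no telephone call, no test of clinical need and no record in the trial.

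Levels would plausibly be requested more often in participants suspected of not taking tablets or doing poorly. If so, the unmasking would be selective rather than random. The same clinician may then decide on new treatment or on stopping a trial drug, and those decisions feed secondary outcomes.

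**Working it through.** No figure in the protocol bears on this point, so the check is a comparison of the text.

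**1. Does *trial drugs* include the masked drugs?** The term is not defined. Section 6, headed Trial Treatments, covers open-label quetiapine and both masked drugs, and 6.1 asks participants to report effects that "might be related to quetiapine, lamotrigine or folic acid". In contrast, 6.6 on the supply of trial treatments lists only lamotrigine and folic acid with their placebos, and 6.2 calls quetiapine standard treatment. A reading confined to quetiapine is therefore not secure. A site could reasonably take the instruction to include lamotrigine or its placebo.

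**2. Does the protocol give a reason to order a level?** The sentence in 3.2 sets drug levels beside adherence. Sections 5.3.1, 5.4.1 and 5.5.1 then ask for adherence to lamotrigine/placebo and folic acid/placebo at 12, 22 and 52 weeks. None of these forms asks for a level.

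**3. What would a result show?**

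| Local result | Possible explanations | Identifies allocation? |
|---|---|---|
| Lamotrigine measurable, no other source | Active lamotrigine | Yes |
| Lamotrigine undetectable | Placebo, or active but not taken | No |
| Folate raised | Folic acid or diet | Suggestive only |

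The condition of no other source matters. Section 3.2.3 allows for lamotrigine treatment before screening, and 6.7.2 provides for local supply after a dose change outside the protocol. On folate, 1.3.5 notes a dietary source: "Folate hydrolase 1 (FOLH1) facilitates the transfer of dietary folate into the body". Folate is therefore present on placebo too, and under 7.4 the investigator does not see the central baseline value for comparison.

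**4. Do the masking rules already close this route?** Section 5.8 governs requests to the trial team, and a local assay involves no such request. Section 5.9 states the aim but does not mention assays. Section 7.4 belongs to the section on the trial's own samples, taken at screening and at 12 weeks (7.1). Nothing extends it to tests ordered locally under 3.2.

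**5. Which outcomes are exposed?** In 3.1.2, outcomes 4 and 5 count new admission or drug treatment, for example "New intervention (admission or drug treatment) for depressive episode by 52 weeks". Outcome 10 counts withdrawal from quetiapine or lamotrigine due to adverse effects. Clinicians influence all three. Section 6.5.6 allows new treatment for depressive symptoms after week 12, so knowledge of allocation could act on outcome 5 from then. The primary outcome is the self-rated QIDS-SR16. Weekly ratings go by SMS, webform or post to the trial system (5.6, 5.7), so any effect on it would be indirect.

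**6. Can the bias be sized?** A simple expression is shift in the arm contrast = (proportion unmasked) × (shift among those unmasked). The protocol gives neither term. If no lamotrigine level is ever taken at a site, the first term is 0 and so is the product. No other value can be supported from the document.

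**The case against.** The strongest reply is that the sentence in 3.2 is a general statement of good care, limited by normal practice, and that 5.9 already states the masking rule. The protocol nowhere says that lamotrigine or folate levels are normal practice, no dosing step in 6.3 uses a serum level, and no follow-up form requests one. All of that stands, and it makes this a permission left open rather than an order to unmask. It does not close the gap, because no section says that the monitoring instruction excludes the masked drugs.

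Several stronger readings are tempting and are not supported:

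- *That the protocol requires unmasking assays.* The reference to normal practice rules this out.
- *That any single lamotrigine or folate level gives the allocation.* Only a measurable lamotrigine level with no other source does.
- *That women on combined oral contraceptives need levels for dosing.* Section 6.3.3 uses a fixed schedule with reduction for tolerability, and its note on adjustment is triggered by the woman reporting that she has stopped the contraceptive.
- *That the primary comparison is biased by a stated number of QIDS points.* Neither input exists in the document. In addition, 6.5.5 and 6.5.6 ask investigators to avoid quetiapine dose changes and added treatment for depressive symptoms in the first 12 weeks.
- *That outcomes 4, 5 and 10 rest on the investigator alone.* Participants may stop treatment for any reason (5.13) or for an adverse event they find intolerable (8.3), and they report new treatment monthly (5.6).

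A further objection is that keeping a clinically needed result from the treating doctor would conflict with the responsibility for care that 3.2 assigns. This also stands, and it limits what the fix should ask for.

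**Conclusion.** The point holds in a limited form. Section 3.2 permits masked investigators to measure a masked drug, and for lamotrigine a measurable level can identify active allocation without passing through 5.8 and without a record. It is an unreconciled gap between 3.2 and sections 3.2.4, 5.8, 5.9 and 7.4.

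The conclusion rests on three assumptions: that some sites read *trial drugs* to include lamotrigine/placebo, that their normal practice includes lamotrigine levels, and that the participant has no other source of the drug. How often these coincide is unknown, so no size of bias is given, and it is nil where levels are not taken. The exposure is mainly to secondary outcomes 4, 5 and 10. Severity is minor to moderate: it is worth correcting because unmasking cannot be reversed, but it does not by itself threaten the primary comparison.

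**What to change.** Reconcile 3.2 with 3.2.4, 5.8, 5.9 and 7.4:

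1. Limit the routine level-monitoring instruction in 3.2 to open-label medicines.
2. State that levels of the masked drugs are not part of routine adherence monitoring by masked staff.
3. Record any locally obtained lamotrigine level as a possible unmasking event, so that its frequency and balance between arms can be reported.

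How a clinically needed assay is handled is for the sponsor to reconcile with 5.8 and with the investigator's duty of care. No rule is proposed here.

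The cost is a short amendment to 3.2, a note to sites and one item to record. The downside is that investigators lose an informal check on adherence to lamotrigine. The emergency route in 5.8 is unaffected.

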#### 4. Selection of Trial Participants

##### 4.1. Inclusion and exclusion criteria for entry to the active run-in phase

Patients must satisfy all the following criteria to be eligible for the run-in phase:

###### 4.1.1. Inclusion criteria:

1. primary diagnosis of bipolar disorder type I or II (based on DSM-IV criteria for a hypomanic or manic episode)
2. consent to participate in the trial
3. aged 16 or over
4. current depressive episode requiring new pharmacological treatment (either as add-on therapy or as a change of treatment)

###### 4.1.2. Exclusion criteria:

1. definite indications or contraindications to lamotrigine, quetiapine or folic acid\* (Including pregnancy and planned pregnancy)
2. new course of a specific psychosocial intervention started in the past 4 weeks
3. first appointment for a specific psychosocial intervention booked within the next 14 weeks
4. In the opinion of the investigator, currently experiencing manic or mixed episode.
5. primary diagnosis of schizophrenia

Plus, for women of child-bearing potential

6. currently breast feeding or not using adequate contraception.

\* Participants who have active cancer, a diagnosed pre-malignant condition, a strong family history of cancer or are unwilling to stop taking folic acid supplements can, where clinically appropriate, be randomised to the lamotrigine/placebo arm (see section 3.2.3.)

---

 Defined as Cognitive Behaviour Therapy (CBT), Group Psychoeducation, Family-focused Therapy and Interpersonal and Social Rhythm Therapy (IPSRT)

#### **4.2. Additional inclusion criteria for entry to the randomised phase**

Patients must satisfy the eligibility criteria above plus all the following criteria to be eligible for entry to the randomised phase:

1. able to tolerate quetiapine at a dose of at least 150mg/day
2. uncertainty whether quetiapine plus lamotrigine would be more effective than quetiapine monotherapy
3. acceptable adherence to quetiapine (>90%) and self-report satisfactory
4. willing to accept random allocation of treatments
5. In the opinion of the investigator, not currently experiencing manic or mixed episode.

